## 2 PROTOCOL SYNOPSIS

**Title** A Phase 2a, 2-part, Randomized, Double-blind, Placebo-controlled, Incomplete Block Crossover Study to Evaluate the Safety and Efficacy of VX-371 Solution for Inhalation With and Without Oral Ivacaftor in Subjects With Primary Ciliary Dyskinesia

**Brief Title** CLEAN-PCD: Clearing Lungs with ENaC Inhibition in Primary Ciliary Dyskinesia

**Clinical Phase and Clinical Study Type** Phase 2a, safety and efficacy

**Objectives** Part A Objectives

**Primary**

To evaluate the safety and efficacy of treatment with VX-371, administered with and without 4.2% hypertonic saline (HS) in subjects with primary ciliary dyskinesia (PCD) who are  $\geq 12$  years of age

**Secondary**

To evaluate the effect of VX-371, administered with and without 4.2% HS, on quality of life (QOL) in subjects with PCD who are  $\geq 12$  years of age

Part B Objectives

**Primary**

To evaluate the safety and efficacy of treatment with ivacaftor and VX-371, administered with and without 4.2% HS in subjects with PCD who are  $\geq 12$  years of age

**Secondary**

To evaluate the effect of ivacaftor and VX-371, administered with and without 4.2% HS on QOL in subjects with PCD who are  $\geq 12$  years of age

[figure not shown]
**Endpoints** Part A Endpoints

**Primary**

- Results of safety and tolerability assessments of adverse events (AEs), clinical laboratory values (urine, serum and plasma chemistry, and hematology), 12-lead electrocardiograms (ECGs), spirometry, vital signs, and pulse oximetry
- Absolute change in percent predicted forced expiratory volume in 1 second (ppFEV1) from study baseline, after 28 days of treatment in Part A

**Secondary**

- Change in QOL score as measured by the Quality of Life-PCD Questionnaire (QOL-PCD) and the St. George's Respiratory Questionnaire (SGRQ) from study baseline, after 28 days of treatment in Part A

[figure not shown]
**Part B Endpoints**

**Primary**

- Results of safety and tolerability assessments of AEs, clinical laboratory values (urine, serum and plasma chemistry, and hematology), 12-lead ECGs, spirometry, vital signs, and pulse oximetry
- Absolute change in ppFEV1 from study baseline and Part B baseline, after 28 days of treatment in Part B

**Secondary**

- Change in QOL score as measured by the QOL-PCD and SGRQ from study baseline and Part B baseline, after 28 days of treatment in Part B

**Number of Subjects** Approximately 150 subjects will be randomized to 1 of 4 treatment sequences

**Study Population** Male and female subjects  $\geq 12$  years of age with a confirmed diagnosis of PCD

**Investigational Drug** Active substance: VX-371  
Activity: Epithelial sodium channel (ENaC) inhibitor  
Strength and Route of Administration: 85  $\mu\text{g}$  VX-371 in 3 mL 0.17% saline, oral nebulized inhalation

Active substance: VX-371 in HS  
Activity: ENaC inhibitor + osmolyte  
Strength and Route of Administration: 85  $\mu\text{g}$  VX-371 + 3 mL 4.2% HS, oral nebulized inhalation

Active substance: HS  
Activity: Osmolyte  
Strength and Route of Administration: 3 mL 4.2% HS, oral nebulized inhalation

Active substance: Not applicable  
Activity: Placebo  
Strength and Route of Administration: 3 mL 0.17% saline, oral nebulized inhalation

Active substance: ivacaftor  
Activity: cystic fibrosis transmembrane regulator (CFTR) potentiator  
Strength and Route of Administration: 150-mg tablet, oral

**Study Duration** **Part A Study Duration**

Excluding the Screening Period, the planned study duration is 113 days from Day 1 to Safety Follow-up Telephone Call, approximately 28 days after the last dose of study drug.

**Part A + Part B Study Duration**

Excluding the Screening Period, the planned study duration is 141 days from Day 1 to Safety Follow-up Telephone Call, approximately 28 days after the last dose of study drug.

**Study Design** Phase 2a, 2-part, randomized, double-blind, placebo-controlled, incomplete block crossover, multicenter study in subjects  $\geq 12$  years of age with PCD. Subjects will be randomized to 1 of 4 treatment sequences as shown in [Table 2-1](#).

**Table 2-1 Study PS-G202 Treatment Sequences**

| Sequence | Part A                 |                        | Part B                             |
|----------|------------------------|------------------------|------------------------------------|
|          | Treatment Period 1     | Treatment Period 2     | Treatment Period 3                 |
| 1        | VX-371 in 4.2% HS      | 4.2% HS                | 4.2% HS + ivacaftor                |
| 2        | 4.2% HS                | VX-371 in 4.2% HS      | VX-371 in 4.2% HS + ivacaftor      |
| 3        | VX-371 in 0.17% saline | Placebo (0.17% saline) | Placebo (0.17% saline) + ivacaftor |
| 4        | Placebo (0.17% saline) | VX-371 in 0.17% saline | VX-371 in 0.17% saline + ivacaftor |

This study includes the following:

- **Screening Period:** Day of Screening Visit until Day 1 (first dose of study drug). The Screening Visit can occur Day -38 to Day -5, relative to the first dose of study drug.
- **Treatment Periods:**
  - **Part A:**
    - Treatment Period 1: Day 1 (first dose of study drug) through Day 29 (28 days of treatment)
    - Washout Period: Day 29 through Day 56 (28 days)
    - Treatment Period 2: Day 57 through Day 85 (28 days of treatment)
  - **Part B (Optional):**
    - Treatment Period 3: Day 85 (first dose of oral ivacaftor) through Day 113 (28 days of treatment)
- **Safety Follow-up Period:** 28 days ( $\pm 7$  days) after the last dose of study drug

If the subject prematurely discontinues study drug, an Early Termination of Treatment (ETT) Visit should be scheduled as soon as possible after the subject decides to terminate study drug treatment. Subjects who prematurely discontinue treatment will also be required to complete the Safety Follow-up Telephone Call approximately 28 days ( $\pm 7$  days) after their last dose of study drug.

**Assessments** Efficacy: spirometry, QOL-PCD, SGRQ

Safety: AEs, spirometry, clinical laboratory values (urine, serum and plasma chemistry, and hematology), ECGs, vital signs, and pulse oximetry

[REDACTED]

**Statistical Analyses** Statistical analysis details will be provided in the statistical analysis plan (SAP), which will be finalized before the clinical database lock for the study.

**Part A**

The primary efficacy objective of Part A is to evaluate the efficacy of VX-371 with and without HS in subjects  $\geq 12$  years of age with PCD. For the Part A efficacy analysis, statistical inferences will be based on change from study baseline, and formal comparisons will be made between groups. The null hypotheses to be tested in Part A are that the absolute absolute change from study baseline in ppFEV1 after 28 days of treatment is the same for 1) VX-371 in HS versus placebo; 2) VX-371 versus placebo; and 3) VX-371 in HS versus HS alone.

To have a feasible sample size and study duration, Part A of this study uses a crossover design. Assuming a standard deviation of 7 percentage points, 50 subjects each for Treatment Sequence 1 and 2 are needed to have approximately 81% power to detect a 3-percentage point treatment difference in the mean absolute change in ppFEV1 from study baseline, after 28 days of treatment between VX-371 + HS and HS alone. Part A of the study will have approximately 87% power to detect a 4-percentage point change from baseline, after 28 days of treatment in ppFEV1 between VX-371 + HS and placebo. The power to detect a 3 percentage point difference between VX-371 and placebo is about 51%. The sample size estimate was based on 10000 simulation runs with an incomplete block design assuming no dropouts. In the simulation, the correlation between responses to the 2 treatments within a subject was assumed to be 0. Furthermore, a 2-sided significance level of 0.05 was used in the sample size determination with no multiplicity adjustment. The sample size also takes into consideration an assumed dropout rate of 10%.

The primary efficacy endpoint is the absolute change in ppFEV1 from study baseline, after 28 days of treatment in each Treatment Period of Part A. The primary efficacy analysis is based on a mixed-effects model. This model will include the absolute change from study baseline in ppFEV1 after 28 days of treatment as the dependent variable, treatment and period as fixed effects, and subject as a random effect. The within-subject covariance will be assumed to have the compound symmetry (CS) structure. Denominator degrees of freedom for the F-test for fixed effects will be estimated using the Kenward-Roger approximation.

The estimated mean of the dependent variable, a 95% confidence interval (CI), and a 2-sided *P* value will be provided for each treatment. There will be no adjustment for multiplicity. Similarly, the estimated between-treatment differences along with the corresponding 95% CI and 2-sided *P* values will be presented.

**Part B**

For the Part B primary efficacy endpoints, absolute change in ppFEV1 from study baseline and Part B baseline, after 28 days of treatment, descriptive summary statistics (n, mean, SD, SE, median, minimum, and maximum), and within-group comparisons will be made.

The within-group *P* value and the 95% CI based on normal approximation will be provided for absolute change in ppFEV1:

- From study baseline, after 28 days of treatment in Part B
- From Part B baseline, after 28 days of treatment in Part B

**IDMC Reviews** The independent data monitoring committee (IDMC) will conduct regular planned safety reviews of study as described in the IDMC charter.

### 3 SCHEDULE OF ASSESSMENTS

Schedules of Assessments are shown in [Table 3-1](#), [Table 3-2](#), and [Table 3-3](#).

**Table 3-1 Study PS-G202: Screening Period**

| Event/Assessment                                 | Screening Period
(Day -38 to Day -5)  |
|--|--|
| Clinic visit                                     | X  |
| Informed consent/assent                          | X  |
| Inclusion/exclusion criteria review a | X  |
| Demographics                                     | X  |
| Medical history                                  | X  |
| Medications review                               | X  |
| Height and weight b                   | X  |
| Pulse oximetry and vital signs c      | X  |
| Full physical examination d           | X  |
| 12-lead ECG e                         | X  |
| Spirometry f                          | X  |
| Single dose of HS to assess tolerability         | X  |
| Serum $\beta$ -HCG g                  | X  |
| Serum FSH h                           | X  |
| Serum chemistry                                  | X  |
| Plasma chemistry i                    | X  |
| Hematology                                       | X  |
| PCD genotype j                        | X  |
| Urinalysis                                       | X  |
| Adverse events and serious adverse events        | Continuous from signing of ICF/assent (if applicable) and initiation of study procedures through the Safety Follow-Up Telephone Call |

- a After obtaining informed consent/assent, inclusion criteria # 4A and # 4B ([Section 9.1](#)), as applicable, must be confirmed prior to initiating any other screening assessments during the Screening Period.
- b Height and weight will be measured with shoes off. BMI will be calculated.
- c Pulse oximetry and vital signs will be performed after the subject has been seated or supine for at least 5 minutes.
- d Physical examination of all body systems, excluding rectal and genitourinary examinations.
- e The ECG will be performed after the subject has been seated or supine for at least 5 minutes. Prior to placing ECG leads, the record will be reviewed for the presence of dextrocardia. Subjects with dextrocardia will have all ECG limb and chest (V) leads reversed.
- f The spirometry assessment will be performed within 60 minutes before the test dose of HS and 60 minutes ( $\pm$  5 minutes) after the test dose of HS. See [Section 8.1.1](#) for more information.
- g A serum pregnancy test will be performed for all female subjects of childbearing potential.
- h Follicle-stimulating hormone (FSH) will be measured for any suspected postmenopausal female with at least 12 months of continuous spontaneous amenorrhea. Serum FSH levels must be  $\geq$ 40 mIU/mL to be considered postmenopausal.
- i Plasma potassium.
- j Unless a confirmed PCD genotype is an inclusion criterion for a particular subject (see [Section 9.1](#)), the genotype result is not required in order for randomization to occur.

**Table 3-2 Study PS-G202: Treatment Period**

| Event/Assessment                        | Part A                                       |  |  |   |   | Part B  |                             |   |  |   |   |                             |                             |  |  |                               |
|---|--|--|--|---|---|---|-----------------------------|---|--|---|---|-----------------------------|-----------------------------|--|--|-------------------------------|
|   | Treatment Period 1
(Day 1 through Day 29) |  |  |   | Washout
Day 29 to
Day 56
(+3 Days) | Treatment Period 2
(Day 57 through Day 85) |                             |   |  | Treatment Period 3 a
(Day 85 through Day 113) |   |                             |                             |  |  |                               |
|   | Day 1
(±1 Day)                            | Day 4
Telephone
Call
(±1 Day) | Day 15 b
Telephone
Call
(±1 Day) | Day 15 b
Visit
(±3 Days) |   | Day 29
Visit
(±3 Days)                  | Day 57
Visit
(±1 Day) | Day 60
Telephone
Call
(±1 Day) | Day 71 b
Telephone
Call
(±1 Day) | Day 71 b
Visit
(±3 Days)                   | Day 85 c
Visit
(±3 Days) | Day 86
Telephone
Call | Day 87
Telephone
Call | Day 99 b,d
Telephone
Call
(-11 Days) | Day 99 b,d
Visit
(-11 Days) | Day 113
Visit
(±3 Days) |
| Pre-visit reminder contact e | X  |  |  |   | X   | X   |                             |   |  | X   |   |                             |                             |  |  | X                             |
| Part B informed consent/assent          |  |  |  |   |   | X f                                |                             |   |  |   |   |                             |                             |  |  |                               |
| Clinic visit                            | X  |  |  | X   | X   | X   |                             | X                                       | X  |   |   |                             |                             | X  |  | X                             |
| Safety telephone call g      |  | X                                      | X  |   |   |   | X                           | X                                       |  |   | X   | X                           | X                           |  |  |                               |
| Inclusion/exclusion criteria review     | X  |  |  |   |   |   |                             |   |  |   |   |                             |                             |  |  |                               |
| Randomization h              | X  |  |  |   |   |   |                             |   |  |   |   |                             |                             |  |  |                               |
| Medical history                         | X  |  |  |   |   |   |                             |   |  |   |   |                             |                             |  |  |                               |
| QOL-PCD i                    | X  |  |  |   | X   | X   |                             |   | X  |   |   |                             |                             |  |  | X                             |
| SGRQ i                       | X  |  |  |   | X   | X   |                             |   | X  |   |   |                             |                             |  |  | X                             |

a Subjects will sign a new ICF (or assent if applicable) before the Day 85 Visit in order to continue into Treatment Period 3. If the subject does not sign the new ICF, Treatment Period 2 will end at Day 85 and the subject will continue through to the Safety Follow-up Telephone Call.

b Day 15, Day 71, and Day 99 clinic visit required for subjects randomized prior to IDMC approval to change visit to a telephone call.

c At the Day 85 Visit, subjects will remain in clinic for a total of 2 to 4 hours after dosing with study drug. The duration of the extended time for each subject (2 to 4 hours) will be left up to the discretion of the investigator. Post-dose safety assessments will be done prior to discharge from the clinic.

d Day 99 Visit or telephone call may occur any time between Day 88 and Day 99. The clinic visit may be changed to a telephone call after approval from the IDMC.

e Pre-visit reminder should be done 1 day before the visit, via telephone call, email, or text message, to remind subject to withhold short-acting bronchodilators for 4 hours prior to spirometry assessment performed at each visit, to withhold long-acting bronchodilators the night before the visit, and to administer study drug at least 4 hours before visits on Day 29, Day 85, and Day 113.

f Subjects who participate in Part B will sign a new ICF for Treatment Period 3. This should occur at least 2 weeks prior to Day 85 to allow for delivery of study drug for Treatment Period 3.

g A safety telephone call will occur on Day 4, Day 15 (if no visit conducted), Day 60, Day 71 (if no visit conducted), Day 86, Day 87, and between Day 88 and Day 99 (if no Day 99 Visit conducted) for safety purposes (e.g., inquiry about adverse events). The telephone call on Day 86 and 87 will continue until the IDMC deems them unnecessary.

h Randomization will occur once it is confirmed that the subject meets all eligibility criteria, and approximately 5 to 10 days prior to Day 1, in order for study drug to be delivered to the site and in time for the first dosing.

i The QOL-PCD assessment must be completed before the start of any other assessments scheduled at this visit. The SGRQ should be completed immediately following the QOL-PCD assessment and before the start of other assessments.

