#### 8.1.3.1 Part A

Part A comprises Treatment Period 1, the Washout Period, and Treatment Period 2.

##### 8.1.3.1.1 Treatment Period 1

At the Day 1 Visit, the subject is required to continue to meet all inclusion and exclusion criteria ([Sections 9.1](#) and [9.2](#)) and continue to have stable PCD disease, in the opinion of the investigator. The first dose of inhaled study drug will be administered after randomization on Treatment Period 1 Day 1. Inhaled study drug should be taken according to instructions provided within the protocol. Study clinic visits will occur on Day 1 and Day 29 to allow for a full 28 days of treatment.

If the first dose of inhaled study drug administered in the clinic on Day 1 is taken in the morning, the second dose will be taken that evening. The last dose of the twice daily study regimen will be taken on the evening of Day 28 and no dose will be taken before the morning visit on Day 29.

If the first dose of inhaled study drug on Day 1 is taken in the clinic in the afternoon, a second dose will not be taken that evening. The last dose of the twice daily study regimen in Treatment Period 1 will be taken on the morning of Day 29, at least 4 hours before the Day 29 Visit.

Subjects should only take the inhaled study drug at a maximum of twice daily.

At Day 4 ( $\pm 1$  day), subjects will have a telephone call from the study coordinator or authorized site designee for safety purposes to ascertain if there have been any AEs. If necessary to follow up on a new medical problem, the subject may be asked to return to clinic.

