**8.1.3.1.3 Treatment Period 2**

In order to continue into Treatment Period 2, subjects must not have an acute upper or lower respiratory infection, pulmonary exacerbation, or changes in therapy (including antibiotics) for pulmonary disease within 28 days before the Day 57 Visit. If the subject does not meet these criteria, then the continuation of the subject into Treatment Period 2 should be discussed with the Parion medical monitor.

The first dose of inhaled study drug in Treatment Period 2 will be administered at the Day 57 Visit.

Study clinic visits will occur on Day 57 and Day 85 to allow for a full 28 days of treatment. If the dose of inhaled study drug administered in the clinic on Day 57 is taken in the morning, the second dose of inhaled study drug will be taken that evening. The last dose of the twice daily study regimen will be taken on the evening of Day 84 and no dose will be taken before the morning visit on Day 85.

If the first dose of inhaled study drug on Day 57 is taken in the clinic in the afternoon, a second dose of inhaled study drug will not be taken that evening. The last dose of the twice daily study regimen in Treatment Period 2 will be taken on the morning of Day 85, at least 4 hours before the Day 85 Visit.

Subjects should only take the inhaled study drug at a maximum of twice daily.

On Day 60, subjects will have a telephone call for safety purposes (e.g., inquire about adverse events). If necessary to follow up on a new medical problem, the subject may be asked to return to clinic.

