### 8.1.3.2 Part B

Part B comprises Treatment Period 3 and is optional.

#### 8.1.3.2.1 Treatment Period 3

In order to continue into Treatment Period 3 the subject must sign the Part B informed consent form (ICF) or assent, as applicable. The ICF should be signed before the Day 85 Visit to allow for delivery of study drug for Treatment Period 3.

Study visits will occur on Day 85 (also the last visit of Treatment Period 2) and Day 113 to allow for a full 28 days of study drug (inhaled study drug and oral ivacaftor).

On Day 86 and Day 87, until the telephone call is no longer required by the IDMC, subjects will have a telephone call for safety purposes (e.g., inquire about AEs). If necessary, the subject may be asked to return to clinic to follow up on a new medical problem.

The first dose of both ivacaftor and inhaled study drug in Treatment Period 3 will be administered at the Day 85 Visit, after completion of the Day 85 pre-dose assessments.

If the first dose of study drug (inhaled study drug and oral ivacaftor) administered in the clinic on Day 85 is taken in the morning, the second dose will be taken that evening. The last home dose of the twice daily study regimen in Treatment Period 3 will be taken on the evening of Day 112 and no dose will be taken on Day 113.

If the first dose of study drug (inhaled study drug and oral ivacaftor) administered in the clinic on Day 85 is taken in the afternoon, a second dose will not be taken that evening. The last home dose of the twice daily study regimen in Treatment Period 3 will be taken on the morning of Day 113, at least 4 hours before the Day 113 Visit.

Subjects should only take study drug at a maximum of twice daily.

Subjects will remain in the clinic for a total of 2 to 4 hours after dosing with study drug at the Day 85 Visit until the IDMC provides approval to only require subjects to remain in clinic for 1 hour post-dosing. The duration (2 to 4 hours) each subject stays in clinic for observation will be left to the discretion of the investigator. If the IDMC does not approve reducing the observation period to 1 hour post-dosing, then subjects will continue to be observed in clinic for 2 to 4 hours during the Day 85 Visit.

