#### **10.2.4 Dosing at Home**

If the first dose of study drug administered in the clinic on Day 1, Day 57, or Day 85 is taken in the morning, the second dose will be taken that evening. The last dose of the twice daily study regimen will be taken on the evening of Day 28, Day 84, or Day 112 and no dose will be taken before the morning visit on Day 29, Day 85, or Day 113.

If the first dose on Day 1, Day 57, or Day 85 is taken in the clinic in the afternoon, a second dose will not be taken that evening. The last dose of the twice daily study regimen will be taken on the morning of Day 29, Day 85 or Day 113, at least 4 hours before the afternoon visit on Day 29, Day 85, or Day 113.

Subjects will be instructed to administer the study drug (inhaled study drug and/or oral ivacaftor) twice daily approximately 12 hours apart. Whenever possible, subjects should take the study drug at the same time each day. For example, the morning dose could be taken at 8:00 AM every morning and the evening dose could be taken at 8:00 PM every evening.

All inhaled study drug will be administered twice daily via the PARI eFlow nebulizer over an estimated 6 to 8 minutes.

Subjects will be asked to record the time start and stop of study drug dosing in a subject diary provided to them at Day 1, Day 57, and Day 85.

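### The pre-visit dosing reminder is scripted two ways (Table 3-2 footnote e and Section 8.1.3.3), and neither fully matches the dosing rule for morning visits

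*Protocol*

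**What the plan says.** Three sets of protocol text govern dosing before the end-of-period visits.

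- **Table 3-2, footnote e.** The contact made the day before the visit reminds the subject "to administer study drug at least 4 hours before visits on Day 29, Day 85, and Day 113". It makes no distinction between morning and afternoon visits. SAP Appendix IV, Table 6, repeats the footnote but does not direct sites.
- **Section 8.1.3.3, first bullet.** This describes the same contact. The morning dose is to be held back only where the visit is booked within 4 hours of it.
- **Section 10.2.4, with 8.1.3.1.1, 8.1.3.1.3 and 8.1.3.2.1.** The rule follows the time of the period's first clinic dose. After a morning start the last dose is the evening before, and "no dose will be taken before the morning visit on Day 29, Day 85, or Day 113". After an afternoon start ("If the first dose on Day 1, Day 57, or Day 85 is taken in the clinic in the afternoon") the last dose is on the morning of the end visit, at least 4 hours ahead of it.

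Day 85 is special because it closes Period 2 and opens Part B: "The first dose of both ivacaftor and inhaled study drug in Treatment Period 3 will be administered at the Day 85 Visit". If that clinic dose "is taken in the morning, the second dose will be taken that evening". Sections 8.1.3.1.3 and 8.1.3.2.1 both cap dosing at twice a day.

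**The concern.** The reminder is the last instruction a subject hears before the visit, and it has two scripts. Footnote e sets an instruction to administer beside two instructions to withhold bronchodilators, so it is easily taken as an action for the visit day. Section 8.1.3.3 gives a conditional instruction that depends on the interval from dose to visit. The dosing section uses neither test.

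Two things are at stake. The first is dosing on Day 85: a home dose, followed by a morning clinic dose and the evening dose that Section 8.1.3.2.1 then requires, exceeds the daily maximum on the day ivacaftor starts. The second is consistency of measurement. Day 29 and Day 85 supply the Part A primary ppFEV1 values (SAP Section 8.1), and Day 113 supplies the Part B value. Subjects with similar visit times could be measured at quite different intervals after their last dose, depending on which text the site followed. Section 11.1 would not catch this, because it accepts a visit once 4 hours have passed since the morning dose.

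**Working it through.** The plan gives no figure to reproduce. The check compares the rules and counts doses and hours.

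**Inputs.** Twice-daily dosing about 12 hours apart, with an 8:00/20:00 example (10.2.4); 4-hour interval (footnote e, 8.1.3.3, 11.1); clinic dose on Day 85 and evening dose after a morning clinic dose (8.1.3.2.1); 85 µg VX-371 per dose. Assumptions: noon divides morning from afternoon, and the early dosing clock is 06:00/18:00. The documents state neither.

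**1. Where 8.1.3.3 and 10.2.4 part.** Let m be the usual morning dose time, m + 12 the evening dose time and v the time of a morning visit (v < 12), for a subject who started the period in the morning.

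- 10.2.4: no dose that morning. Time since last dose = v + 24 − (m + 12) = v − m + 12.
- 8.1.3.3: no dose that morning only if v − m is within 4. Otherwise the dose is taken, and time since last dose = v − m.

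The rules part only when v − m > 4 with v < 12, which requires m earlier than 8:00. When they part, the difference is always (v − m + 12) − (v − m) = 12 hours.

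**2. Protocol example, 8:00/20:00.** Every visit before noon is less than 4 hours after 8:00, so both rules withhold. For visits at 08:00, 09:00, 10:00 and 11:00, time since last dose is v + 24 − 20 = 12, 13, 14 and 15 hours under both. For an afternoon starter with, say, a 13:00 visit, 13 − 8 = 5 hours, and both rules have the dose taken.

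**3. Early clock, 06:00/18:00, visit at 11:00.** 8.1.3.3: 11 − 6 = 5, which exceeds 4, so the dose is taken and the gap is 5 hours. 10.2.4: no dose, and the gap is 11 + 24 − 18 = 17 hours.

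**4. Inhaled doses on Day 85 for that subject entering Part B (home + clinic + evening).**

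| Rule followed | Clinic dose before noon | Clinic dose after noon |
|---|---|---|
| 8.1.3.3, or footnote e read as a home dose | 1 + 1 + 1 = 3 | 1 + 1 + 0 = 2 |
| 10.2.4 | 0 + 1 + 1 = 2 | 0 + 1 + 0 = 1 |

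The cap is exceeded only in the upper left cell. In Sequences 2 and 4, which receive VX-371 in Period 3, that is 3 × 85 = 255 µg against 2 × 85 = 170 µg. In Sequences 1 and 3 the extra dose is hypertonic saline or placebo. Day 29 and Day 113 have no clinic dose, so the cap is not at issue there.

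**5. Footnote e read as a home dose, 8:00/20:00 clock.** For visits at 08:00 to 11:00 the latest home dose is v − 4 = 04:00 to 07:00, only 8 to 11 hours after the evening dose. Read as a minimum gap, the footnote is already met by the evening dose (12 to 15 hours).

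**6. Afternoon Day 57 start, morning Day 85 visit.** Section 8.1.3.1.3 says the last Period 2 dose "will be taken on the morning of Day 85, at least 4 hours before the Day 85 Visit" without saying that the visit must be in the afternoon. Read alone, and with a morning clinic dose, it gives 1 + 1 + 1 = 3. Section 10.2.4 names an afternoon visit in this branch and does not cover the mismatch.

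**The case against.** The strongest reply is that footnote e is loose rather than wrong. As a minimum gap it fits Sections 8.1.3.3, 10.2.5 and 11.1, and it summarises a reminder; the dosing rules are in the body text, which does separate morning from afternoon. That stands: the footnote is ambiguous, and a reader who inferred a flat contradiction would be going beyond the text.

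Second, 8.1.3.3 and 10.2.4 lead to the same action on the protocol's own clock, and the 5 v 17 hour contrast rests on an assumed one. That also stands. But nothing in the protocol prevents a usual dose before 8:00, so the divergent case is allowed.

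Third, there are safeguards. Section 8.1.3 asks for reasonable efforts to hold visits at the same time of day, and Section 11.5.1 asks the same of spirometry relative to baseline, so an afternoon start with a morning end visit departs from the intended schedule. Dose times go into a diary that is collected on Day 85, staff review dosing compliance at visits (10.9), and the twice-daily cap is stated more than once. These make a third dose unlikely. They do not tell the site which reminder to give, and a site that notices the home dose must then choose between breaking the cap and omitting the evening dose.

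**Conclusion.** The inconsistency is real and worth correcting, but the risk is low. Footnote e is ambiguous, and 8.1.3.3 uses a different test from 10.2.4. The two sections conflict only for a late-morning visit that follows a usual dose taken before 8:00. In that case time since last dose differs by 12 hours, given 12-hourly dosing. A Part B entrant whose clinic dose is still given in the morning could take three inhaled doses on Day 85.

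Some stronger conclusions are not supported:

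- A reader might infer bias in the primary comparison. The reminder is the same in every sequence, the inhaled treatment is blinded, and the documents give no ppFEV1 effect for time since last dose. The effect is of unknown size and has no stated direction.
- A reader might take the 50 + 25 = 75 subjects planned for Sequences 2 and 4 as the number at risk of extra VX-371. Part B is optional, and neither its uptake, the share of morning visits nor usual dosing times are given. The number affected cannot be estimated.
- A reader might treat the mismatched start and end times as a routine fault needing a rewrite of all the dosing paragraphs. The scheduling text makes such mismatches exceptions, and one added sentence deals with the case that could breach the cap.

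**What to change.** Replace the dosing part of Table 3-2 footnote e and the first bullet of Section 8.1.3.3 with one text that follows 10.2.4: *Morning visit: last dose the evening before, no dose that morning. Afternoon visit: take the morning dose at least 4 hours before the visit.* Add one sentence: *A subject entering Part B who has a morning Day 85 visit takes no home dose that day, whatever the time of the first dose on Day 57.* Update the SAP copy of the footnote for consistency.

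The cost is wording only: no new visits, data or subjects. Matched schedules keep 56 doses per period: morning to morning 2 + 27 × 2 + 0 = 56, afternoon to afternoon 1 + 54 + 1 = 56. A mismatched subject may get one more or one fewer: morning to afternoon 2 + 54 + 1 = 57, afternoon to morning 1 + 54 + 0 = 55. The 57-dose case is 1 clinic dose plus 56 home doses, which uses the whole 28 × 2 = 56 home supply with none to spare.

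The wording does not guarantee two inhaled doses on Day 85 in every case. A late-morning visit whose clinic dose slips past noon still leaves one, because Section 8.1.3.2.1 then omits the evening dose.
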